- 3.3 Follow-Up: Recall examinations and treatment reapplication will be done at 3 months, 6 months, and 12 months after the initial visit in accordance with current American Academy of Pediatric Dentistry (AAPD) guidelines for high caries risks patients⁵. Bitewing radiographs will be taken at 6 months and 12 months. This is in accordance with the "Prescribing Dental Radiographs..." guidelines as approved by the AAPD²⁰, which state that bitewing radiographs in high risk children with dental caries are recommended every 6-12 months.
- 3.4 Providers: Residents and Attendings at the Ostrow School of Dentistry at USC, Pediatric Residency Program. All residents and attendings participating in this study will be trained and standardized on how to identify lesions of interest on radiographs, obtain consent, and apply the medications.
- 3.5 Tracking of study participants: We will count the number of participants who:
 - 1. Those who are asked to participate
 - 2. Those who consent
 - 3. Those who drop out before randomization/after randomization
 - 4. Those who withdraw by their own choice for various reasons
 - 5. Those who are lost to follow up

Note: We will only collect and store clinical data for those participants who continue throughout the duration of the project. If a participant decides to drop out of the study at any time, then we will no longer collect data from the medical record during their ongoing clinical care. We will also discard any previous data we have collected on the participants that drop out.

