13.0 STATISTICAL CONSIDERATIONS

- 13.1 The proposed pilot Phase III randomized controlled clinical trial aims to determine which of the following treatments is superior in arresting dental caries among patients presenting with interproximal caries scoring RA1 RA3 on the International Caries Classification and Management System (ICCMS): (1) Fluoride varnish (FV, current standard of care, control), (2) Super floss + SDF + FV, (3) SDF + FV. We hypothesize that group 2 will have the best outcomes, as measured by no change or reversal in ICCMS classification indicating no caries progression or remineralization on radiographic examination, (higher score indicates progression) followed by group 3. As we could find no data on ICCMS-defined progression or remineralization rates for either Super Floss or fluoride, we were unable to calculate power. Instead, we provide estimates of recruitment based on feasibility. We expect to accrue approximately 20 participants, with 2 qualifying teeth per participant, in each group.
- 10% loss to follow up has increased dramatically to ~48%. Given this unexpected setback, we now need to continue recruiting participants to reach sufficient power. We originally planned to enroll 39 subjects in the study, but would now like to add 21 new participants for a total of 60 participants.

Descriptive statistics will be calculated for all demographic and clinical characteristics to assess the degree to which randomization was successful using means and standard deviations or medians and interquartile ranges for continuous variables and counts and percentages for categorical variables.

The primary analysis will be by intent-to-treat. The primary outcome is the change in ICCMS category, as assessed by radiographic evidence, from baseline to 12 months, with a planned interim analysis to evaluate the endpoint at 6 months for early indications of efficacy. We will calculate the median difference at each time point and use an individual-level model with an adjustment to the standard error to account for the clustering. First we will evaluate the association between treatment groups and the change in ICCMS score from baseline at 6 and 12 months using a cluster-adjusted chi-squared test. We will further assess

14

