the relationship between these two variables using generalized estimating equations, specifying a Poisson (or negative binomial, if overdispersed) family and a log link. We will also specify an exchangeable correlation matrix and a robust standard error.

Since the study is randomized, we do not anticipate needing to adjust for any confounders. However, should we find any differences in demographic or clinical variables at baseline, we will investigate them as potential confounders, which will be defined as those variables which alter the odds ratio by >15% when included in the model.

For those with missing data on outcomes or other covariates to be included in the model, we will consider multiple imputation methods if the amount of missing data is <10%. To assess the impact of missing data, we will compare those with missing data to those not missing data with respect to demographic and clinical variables to assess comparability. Should imputation be utilized, a sensitivity analysis will be conducted excluding those for whom data was imputed to assess the impact of imputation.

Model fit will be evaluated by inspection of residuals and influential points. As we are conducting an interim analysis, we will use a two-sided Bonferroni-corrected p-value of a=.025 for statistical significance. Finally, to assess the degree to which the two raters agree with respect to classifying the outcome of the x-rays, we will calculate and report Kappa. All statistical analyses will be done using Stata 15.0 (College Station, TX).

Power Analysis

We calculated power using a cluster-randomized design. We were unable to locate any previous studies examining the impact of these three treatments (or any two) using the same classification system as our outcome. However, we were able to obtain an estimate of 0.0 to 0.25 for the interclass correlation coefficient (ICC) (Honkala et al., 2011). Assuming the mean ICC, and assuming a clinically significant mean difference of 0.2, a standard deviation of 0.2, a covariance of cluster sizes of 0.65, two caries on average per child, and a two-sided adjusted Type I error rate of 0.025 to account for the three time points at which the data will be analyzed, we will have 80% power with 11-12 participants per group, for a total of 33-36 participants (66-72 caries). Since we anticipate significant loss-to-follow-up over the course

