of the study, we will inflate the sample size by ~48% and recruit a total of 54-60 participants (108-120 caries). Sample size was calculated using PASS Software v.14.0 (Kayesville, UT).

This study is powered to detect an effect in a population of children who are predominantly non-white. Therefore, the sample size as calculated is likely to result in a sample size with reasonable power to detect an effect near the size outlined above, if perhaps slightly larger.

14.0 REGISTRATION GUIDELINE

- 14.1 Participants will be randomized as described in Section 6.3. Randomization envelopes will be available to the investigators, who need only select the next one in the series to accomplish randomization. No stratification parameters have been specified.
- 14.2 The forms and records needed for registration: Informed Consent; Assentfor Younger Subjects ; and Tracking Form.

Note: At the time of registration, two copies of a signed and dated patient Informed Consent form with Bill of Rights must be available (a copy for patient's dental chart; a copy for the subject/parent; and the original for the PI's file).

15.0 BIOHAZARD CONTAINMENT

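### At the plan's own ~48% loss, 60 recruits leave about 31 evaluable children, below the 33-36 that its 80% power statement requires

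*Combined protocol and SAP*

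**What the plan says.** All the figures are in Section 13.0 (Statistical Considerations) except the dropout rule, which is in Section 3.5.

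- **Requirement.** The Power Analysis states that "we will have 80% power with 11-12 participants per group, for a total of 33-36 participants (66-72 caries").
- **Loss.** Section 13.0 reports that "10% loss to follow up has increased dramatically to ~48" per cent.
- **Recruitment.** The Power Analysis, citing the loss it anticipates, says "we will inflate the sample size by ~48% and recruit a total of 54-60 participants (108-120 caries"). Earlier in Section 13.0, planned enrolment rises from 39: the investigators "would now like to add 21 new participants for a total of 60 participants", so that power is sufficient.
- **Dropouts.** Section 3.5: "We will also discard any previous data we have collected on the participants that drop out".
- **Missing data.** Section 13.0: "we will consider multiple imputation methods if the amount of missing data is <10" per cent.

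**The concern.** A sample that must keep N children after a fraction d is lost has to start at N/(1 − d). The plan names the loss (about 48%) and the number needed (33-36), but its recruitment range does not follow from them, and its target of 60 falls short of the requirement at that loss.

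The plan gives nothing that would recover the lost children. Their data are discarded under Section 3.5, and imputation is considered only when less than 10% is missing.

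Power is the stated reason for enrolling 21 more children. If the enlargement does not bring the evaluable number back to 33-36, that reason fails on the plan's own figures, and 80% is no longer the power the trial should expect.

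**Working it through.** **Inputs (Section 13.0).** Mean difference 0.2; SD 0.2; ICC 0.125, the midpoint of 0.0 and 0.25; two caries per child on average; "a two-sided adjusted Type I error rate of 0.025"; 80% power; loss 48%. The plan gives 0.65 as a covariance of cluster sizes. I read it as a coefficient of variation (CV), which is an assumption, and I also show results without it.

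**Step 1: reproduce the requirement.** With K children per group and two teeth per child, the normal approximation gives K = DE × (2.241 + 0.842)² × (0.2/0.2)² = 9.505 × DE, where DE is the design effect.

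- Without the CV: DE = 1 + (2 − 1) × 0.125 = 1.125, so K = 10.69, or 11 per group.
- With the CV: DE = 1 + ((0.65² + 1) × 2 − 1) × 0.125 = 1.231, so K = 11.70, or 12 per group.

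The plan's 11-12 per group is reproduced, so the fault is in the inflation step.

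**Step 2: try to reproduce 54-60.**

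| Rule | From 33 | From 36 |
|---|---|---|
| Divide by 0.52 | 63.5, so 64 | 69.2, so 70 |
| Multiply by 1.48 | 48.8, so 49 | 53.3, so 54 |
| Plan | 54 | 60 |

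Neither rule gives the plan's range. The loss it implies is 1 − 33/54 = 38.9% and 1 − 36/60 = 40%.

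**Step 3: children retained at 48% loss.**

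- 60 × 0.52 = 31.2 (10.4 per group, about 62 teeth), which is 2-5 children short of 33-36.
- 54 × 0.52 = 28.1 (9.36 per group), which is 5-8 short.
- With 60 enrolled, 33 remain only if loss is at most 1 − 33/60 = 45%, and 36 only if it is at most 40%.
- Reading the 10% as the loss originally planned, 39 × 0.90 = 35.1, which was inside 33-36. The enlarged trial keeps fewer.

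**Step 4: power at the retained number.** Normal approximation: power = Φ(√(K/DE) − 2.241), since difference/SD = 1. The t column uses tooth-level degrees of freedom.

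| Children per group | Normal, DE 1.231 | t, DE 1.231 | Normal, DE 1.125 |
|---|---|---|---|
| 9.36 (54 enrolled) | 69.7% | 66.2% | 74.0% |
| 10.4 (60 enrolled) | 74.7% | 71.7% | 78.8% |
| 11 | 77.3% | 74.5% | 81.2% |
| 12 | 81.1% | 78.7% | 84.7% |

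Compared within a column, 60 enrolled costs about 2-3 points against 11 per group and 6-7 against 12.

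**The case against.** **The 48% may describe only the first 39 children.** Section 13.0 reports it as what loss has risen to, and the start of that sentence appears to be missing from the text available. If the 21 new children were lost at 10%, 39 × 0.52 + 21 × 0.90 = 20.3 + 18.9 = 39.2 would remain, above 36. On this split, 33 is reached if at most 39% of the new children are lost ((33 − 20.28)/21 = 60.6% retained), and 36 if at most 25% are ((36 − 20.28)/21 = 74.9% retained). The point is fair, but the plan does not say this. The Power Analysis applies about 48% to the whole sample because of loss it still anticipates. If a split rate was meant, it needs to be written down.

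**The range may come from multiplying by 1.48.** 36 × 1.48 = 53.3 and 39 × 1.48 = 57.7; rounded up to the randomization blocks of six (Section 6.3), these give 54 and 60. This is a plausible origin, though only an inference. It would not rescue the target, because multiplying by 1 + d does not preserve the number needed.

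**The effect is small and the trial is called a pilot.** This largely stands. At 10.4 per group, the difference detectable with 80% power moves from 0.20 only to 0.203 (DE 1.125) or 0.212 (DE 1.231). The approximation's own uncertainty is of similar size to the loss against 11 per group. This limits how serious the point is. It does not make the numbers agree, and the plan itself uses power to justify more children.

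**Intent-to-treat.** Section 13.0 specifies an intent-to-treat analysis, which sits badly with discarding dropouts' data. Under it, a child seen at 6 months could contribute to the 6-month analysis, but would still have no 12-month outcome.

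**Conclusion.** The concern holds. If about 48% of all recruits are lost, 60 enrolled leaves about 31 evaluable children against a requirement of 33-36, and the low end of 54 leaves about 28. Expected power at 60 is roughly 72-75% with the cluster-size term and about 79% without it; at 54 it is roughly 66-70% and 74% respectively. These figures rest on the plan's own effect size, SD and ICC, on reading 0.65 as a CV, and on 48% applying to old and new recruits alike. They allow nothing for the tooth-level withdrawals in Section 5.3, for which the documents give no rate. The shortfall at 60 is modest, so this should be corrected but does not undermine the design.

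**What to change.** Replace the recruitment sentence in the Power Analysis with wording such as:

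> We will recruit 60 participants (about 120 caries). If about 48% are lost, about 31 children (10-11 per group, about 62 caries) will be evaluable, fewer than the 33-36 required. Sixty recruits retain 33 only if loss is at most 45%, and 36 only if it is at most 40%.

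Then rerun PASS at the retained number and report the result as the expected power, keeping 80% only as the figure for 11-12 evaluable children per group. If a lower loss is assumed for the 21 new children, state the rate and the reason for it. The recruited count of 108-120 caries is correct for 54-60 children and can stay. In the same edit, align Section 13.1, which still says power could not be calculated.

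The cost is one or two sentences and one software run, with no change to enrolment, analysis or conduct. The stated power becomes slightly less favourable.

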Appendix I: Table of the ICCMS Radiographic Scoring System of Carious Lesions								
	ICDAS Radiographic scoring system							
	0	No radiolucency	JU	No radiolucency				
		RA 1		Radiolucency in the outer ½ of the enamel				
dories	RA: Initial stages	RA 2	0	Radiolucency in the inner ½ of the enamel ± EDJ (enamel-dentin junction)				
TM Caries Categories		RA 3		Radiolucency limited to the outer 1/3 of dentin				
ICCMSTM	RB: Moderate stages	RB 4	0	Radiolucency reaching the middle 1/3 of dentin				
	RC:	RC 5		Radiolucency reaching the inner 1/3 of dentin, clinically cavitated				
	Extensive stages	RC 6		Radiolucency into the pulp, clinically cavitated				

Red box encloses Categories 1-3, which are the target lesions for this study.

Version date: 07/31/22
